## 4. OBJECTIVE(S) AND ENDPOINT(S)

Objectives	Endpoints
Primary	
To assess the safety and tolerability of RVT-1401 in AChR antibody positive MG patients over a 6-week treatment period	Assessment of safety and tolerability by analysis of AE data and changes from baseline in vital signs, clinical laboratory values, and electrocardiograms
To examine the effects of RVT-1401 on total IgG, IgG subclasses (1-4) and anti-AChR-IgG levels	Change from baseline in levels of total IgG and IgG subclasses (1-4) Change from baseline in levels of anti-AChR-IgG
Secondary	
To examine RVT-1401 PK following repeat doses in patients with Myasthenia Gravis (MG)	PK Parameters of AUC (0-168 h) and maximum concentration (Cmax) after first and last dose  Concentration of RVT-1401 pre-dose (Ctrough)
To measure anti-RVT-1401 antibodies following repeat doses in patients with MG and assess any potential impact on PK or PD	Immunogenicity determined by change from pre-dose in anti-RVT-1401 antibodies, characterization of any anti-RVT-1401 to confirm neutralization potential
To examine the effects of RVT-1401 on the Quantitative Myasthenia Gravis (QMG) score	Change from baseline in the QMG Score
To examine the effects of RVT-1401 on the proportion of patients with improvement on the QMG score by $\geq 3$ points from baseline	Proportion of participants with an improvement on the QMG score by $\geq 3$ points from baseline
To examine the effects of RVT-1401 on Myasthenia Gravis-Activities of Daily Living score (MG-ADL)	Change from baseline in the MG-ADL score
To examine the effects of RVT-1401 on the proportion of participants with an improvement on the MG-ADL Score by $\geq 2$ points	Proportion of participants with an improvement on the MG-ADL Score by $\geq 2$ points

To examine the effects of RVT-1401 on the Myasthenia Gravis Composite (MGC) score	Change from baseline in the MGC score
To examine the effects of RVT-1401 on the proportion of participants with an improvement on the MGC Score by $\geq 3$	Proportion of participants with an improvement on the MGC Score by $\geq 3$ points
To examine the effects of RVT-1401 on the Myasthenia Gravis Quality of Life (MG-QOL15r) score	Change from baseline in the MG-QOL15r score

### **Open-Label Extension Objective:**

The objective of the OLE is to evaluate the effect of switching to a every 2-week dosing regimen of 340 mg RVT-1401 on all study endpoints.

## **5. STUDY DESIGN**

### **5.1. Overall Design**

This is a Phase 2a, randomized, double-blind, placebo-controlled study with an OLE designed to investigate the safety, tolerability, PK, PD, and efficacy of RVT-1401 (340 mg/weekly and 680 mg/weekly) vs placebo in AChR antibody positive MG patients. Following a 6-week double-blind, placebo-controlled phase, all participants will have the option to enter an OLE where they will receive an additional 3 doses of 340 mg RVT-1401 every 2 weeks for 6 weeks. The study designs are illustrated in Section 5.2.

Safety, PK, PD, and clinical assessments will be collected throughout the study. Refer to Section 8.1 and 8.2, Time and Events Tables.

Optional home visits will be offered to collect (at a minimum) blood samples, vital signs, and review adverse events and concomitant medications.

Each participant will participate in the study for up to approximately 21 weeks: a 3-week screening period, and a 6-week double-blind, placebo-controlled treatment period. Participants who choose not to enroll into the OLE will continue into a 12-week follow-up period. Those who choose to enroll into the OLE will receive treatment in a 6-week OLE period (3 additional doses, every 2 weeks), and a 6-week follow up period. The study duration is the same whether a participant continues directly into the 12-week follow-up period or enrolls into the OLE.

### **Randomized, Double-Blind, Placebo-Controlled Phase**

Participants will screen to determine eligibility up to 21 days prior to first dose/baseline visit. Once eligibility is confirmed, participants will be randomized on Day 1 to receive one of two dose regimens or placebo for weekly SC injections in addition to their standard of care therapy for 6 weeks. No dose adjustments of RVT-1401 are allowed during the study. See Section 6.9 for additional information on stopping criteria.

Following the initial dose at the Baseline Visit (Day 1), study visits will occur at Days 3 and 5 and then weekly throughout the treatment period.

After Week 6, if the participant chooses not to enroll into the OLE, they will continue with the 12-week follow up period.

### **Transition Phase: Option to Enroll into OLE**

Participants will have the option to continue with the follow up period or enroll into the OLE (described below) upon completion of the randomized, double-blind, placebo-controlled phase of the study (Week 6). To enroll into the OLE, consent must be obtained prior to the Week 8 visit.

[figure not shown]
The visit schedule will be the same for either option as outlined in Section 5.2; two study visits will occur at Days 38 and 40, and then weekly through Week 10 and then every 2 weeks until Week 18.

### **Open-Label Extension**

If the participant is eligible and consents to enroll into the OLE, starting at Week 8 an additional 3 doses of 340 mg RVT-1401 will be administered over a 6-week period (every 2 weeks) followed by a 6-week follow up period.

## 5.2. Study Schematics

**Figure 2** Study Design without OLE

**Figure 3** Study Design with OLE

## 5.3. Treatment Arms and Duration

In the double-blind phase of the study, participants will be randomized 1:1:1 to one of the three blinded treatments illustrated in Figure 2.

In the OLE an additional 3 doses over a 6-week period (every 2 weeks) will be administered, illustrated in Figure 3.

## 6. PARTICIPANT POPULATION

### 6.1. Type and Number of Participants

A sufficient number of participants will be enrolled to achieve approximately 21 evaluable participants. Enrollment is competitive.

In order to manage the total study enrollment, the Sponsor may suspend screening and/or enrolment at any site or study-wide at any time.

If participants prematurely discontinue the study, additional replacement participants may be enrolled at the discretion of the Sponsor.

Deviations from inclusion and exclusion criteria are not allowed because they can potentially jeopardize the scientific integrity of the study, regulatory acceptability or participant safety. Therefore, adherence to the criteria as specified in the protocol is essential.

To determine participant eligibility at screening, a single repeat of certain tests such as laboratory values, vital signs, or ECGs is allowed at the discretion of the Principal Investigator.

### 6.2. Inclusion Criteria

A participant will be eligible for inclusion in this study only if all of the following criteria apply:

1. Male or female  $\geq 18$  years of age.
2. Myasthenia Gravis Foundation of America (MGFA) Class II-IVa and likely not in need of a respirator for the duration of the study as judged by the Investigator.
3. Positive serologic test for anti-AChR antibodies at the screening visit and at least 1 of the following:
  - a. History of abnormal neuromuscular transmission test demonstrated by single-fiber-electromyography or repetitive nerve stimulation OR
  - b. History of positive edrophonium chloride test OR
  - c. Participant has demonstrated improvement in MG signs on oral cholinesterase inhibitors as assessed by the treating physician.
4. QMG score  $\geq 12$  at Screening and Baseline.
5. Stable dose of MG treatment prior to randomization. For participants receiving AZA, other non-steroidal immunosuppressive agents, steroids, and/or cholinesterase inhibitors as concomitant medications the following conditions will apply:
  - a. AZA: treatment initiated at least 12 months ago and no dose changes in the last 6 months before Screening.

- b. Other immunosuppressive treatment (e.g., methotrexate, cyclosporine, mycophenolate mofetil, and cyclophosphamide) initiated at least 6 months ago and no dose changes in the last 3 months before Screening.
  - c. Stable dose of steroid treatment at least 6 weeks before Baseline.
  - d. Cholinesterase inhibitors: stable dose for >1 week before Screening. Note: cholinesterase inhibitors must be held for at least 12 hours consistent with the revised manual for the QMG test as recommended by the MGFA, before the QMG and MGC assessments.
6. A female participant is eligible to participate if she is of:
- a. Non-childbearing potential defined as pre-menopausal females with a documented bilateral tubal ligation, bilateral oophorectomy (removal of the ovaries) or hysterectomy; hysteroscopic sterilization, or postmenopausal defined as 12 months of spontaneous amenorrhea [in questionable cases a blood sample with simultaneous follicle stimulating hormone (FSH) in the post-menopausal range is confirmatory].
  - b. Child-bearing potential and agrees to use one of the contraception methods listed in Section 6.6.1 for an appropriate period of time (as determined by the product label or Principal Investigator) prior to the start of dosing to sufficiently minimize the risk of pregnancy at that point. Female participants must agree to use contraception until 90 days after the last dose of study treatment.
7. Male participants must agree to use one of the contraception methods listed in Section 6.6.1. This criterion must be followed from the time of the first dose of study treatment until 90 days after the last dose of study treatment.
8. Willing and capable of giving written informed consent, which includes compliance with the requirements and restrictions listed in the consent form.

### **6.3. Exclusion Criteria**

A participant will not be eligible for inclusion in this study if any of the following criteria apply:

- 1. Use of rituximab, belimumab, eculizumab or any monoclonal antibody/Fc-fusion biologic for immunomodulation within 6 months prior to first dosing.
- 2. Use of tacrolimus within 1 week of first dose and throughout the treatment period.
- 3. Immunoglobulins given by SC, IV (IVIG), or intramuscular route, or plasmapheresis/plasma exchange (PE) within 4 weeks before Screening.
- 4. Thymectomy performed < 12 months prior to screening.
- 5. Total IgG level <6 g/L (at screening).
- 6. Absolute neutrophil count <1500 cells/mm^3(at screening).

7. Participant has any laboratory abnormality (at screening) that, in the opinion of the investigator, is clinically significant, has not resolved at baseline, and could jeopardize or would compromise the participant's ability to participate in this study.
8. Have known autoimmune disease other than MG that would interfere with the course and conduct of the study (such as uncontrolled thyroid disease).
9. Medical history of primary immunodeficiency, T-cell or humoral, including common variable immunodeficiency.
10. Have an active infection, a recent serious infection (i.e., requiring injectable antimicrobial therapy or hospitalization) within the 8 weeks prior to Screening.
11. History of or known infection with human immunodeficiency virus (HIV), hepatitis B virus (HBV), hepatitis C virus (HCV), or *Mycobacterium tuberculosis*.  
Participants must have negative test results for HBV surface antigen, HBV core antibody, HCV antibody, HIV 1 and 2 antibodies, and a negative QuantiFERON®-TB Gold test at Screening. Participants with an indeterminate QuantiFERON®-TB Gold test result will be allowed one retest; if not negative on retesting, the participant will be excluded.
12. Participant has any clinically significant history of allergic conditions (including drug allergies, anaphylactic reactions), that would in the opinion of the Investigator or Medical Monitor, contraindicates their participation.
13. Participant has any medical condition (acute or chronic illness) or psychiatric condition that, in the opinion of the investigator, could jeopardize or would compromise the participant's ability to participate in this study
14. Body Mass Index (BMI) at Screening  $\geq 35 \text{ kg/m}^2$ .
15. Use of investigational drug within 3 months or 5 half-lives of the drug (whichever is longer) before Screening.
16. Currently participating or has participated in another MG clinical study within 28 days prior to signing the informed consent form.
17. Participant has received a live vaccination within 8 weeks prior to the Baseline Visit; or intends to have a live vaccination during the course of the study or within 7 weeks following the final dose of study treatment.
18. Participant has received a transfusion of any blood or blood products within 60 days or donated plasma within 7 days prior to Day baseline.
19. History of sensitivity to any of the study treatments, or components thereof or a history of drug or other allergy that, in the opinion of the Investigator or Medical Monitor, contraindicates their participation.
20. Pregnant or lactating females as determined by positive serum or urine human chorionic gonadotropin test at screening or baseline.
21. Participant has had their spleen removed.
22. QTcF interval  $>450$  milliseconds for males and  $>470$  milliseconds for females at Screening (a single repeat is allowed for eligibility determination). QTcF  $>480$  msec

in participants with Bundle Branch Block.

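### Exclusion 3 looks back from Screening only, so IVIG or plasma exchange in the up to 21 days before first dose does not exclude, although Day 1 IgG is the denominator of the primary endpoint

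*Protocol*

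**What the plan says.** - **Exclusion 3** (Protocol 6.3) bars "Immunoglobulins given by SC, IV (IVIG), or intramuscular route, or plasmapheresis/plasma exchange (PE) within 4 weeks before Screening".
- **Screening interval** (Protocol 5.1): "Participants will screen to determine eligibility up to 21 days prior to first dose/baseline visit".
- **Exclusion 10** (Protocol 6.3): "Have an active infection, a recent serious infection (i.e., requiring injectable antimicrobial therapy or hospitalization) within the 8 weeks prior to Screening". The look-back for serious infection ends at Screening. The active-infection limb has no time anchor.
- **Inclusion 5** (Protocol 6.2): the stem requires stable MG treatment up to randomization. Sub-item 5a reads "AZA: treatment initiated at least 12 months ago and no dose changes in the last 6 months before Screening", and 5b requires treatment "initiated at least 6 months ago and no dose changes in the last 3 months before Screening". Sub-item 5d (cholinesterase inhibitors) also counts back from Screening, while 5c (steroids) counts back from Baseline.
- **Windows that already run to first dose or Baseline:** exclusions 1 (biologics), 2 (tacrolimus), 17 (live vaccine) and 18. Exclusion 18 reads "Participant has received a transfusion of any blood or blood products within 60 days or donated plasma within 7 days prior to Day baseline" and names neither immunoglobulin nor PE.
- **IgG floor** (exclusion 5): below 6 g/L, applied at screening.
- **Re-check** (Protocol 8.1 and 8.2): eligibility is marked at Screening and again on Day 1.
- **Endpoint** (Protocol 10.3.1; SAP 5.2 and 9.1): percentage change in total IgG from Baseline to Week 7, where Baseline is the last value before first dose.

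**The concern.** Immunoglobulin and PE act directly on circulating IgG, which is what the primary endpoint measures. Either one given shortly before Day 1 disturbs the denominator. Added immunoglobulin raises it, so IgG then falls without study drug. PE lowers it, so IgG then recovers. In a placebo participant the first narrows the apparent drug effect and the second widens it.

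The Day 1 re-check does not close the gap, because the text being re-checked still refers to Screening. The IgG floor does not close it either. PE after Screening could take IgG below 6 g/L with no eligibility criterion applying on Day 1, before a drug expected to lower IgG by roughly two thirds or more (Protocol 3.2.2). Sites are blinded to IgG after screening (Protocol 7.3).

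The protocol gives no reason for ending this window at Screening when several others run to first dose or Baseline.

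**Working it through.** **1. The uncovered interval.** With Screening on Day -s, exclusion 3 covers Day -(s + 28) to Day -s and leaves s days open.

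| Screening | Covered by exclusion 3 | Uncovered days |
|---|---|---|
| Day -7 | Day -35 to -7 | 7 |
| Day -14 | Day -42 to -14 | 14 |
| Day -21 | Day -49 to -21 | 21 |

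The maximum of 21 agrees with the 3-week screening period (3 × 7). With Screening on Day -21, PE on Day -22 excludes and PE on Day -5 does not.

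**2. The other Screening-anchored items, read in full.**
- Exclusion 10: an infection still active on Day 1 excludes, because that limb has no anchor. Exclusion 13, "Participant has any medical condition (acute or chronic illness) or psychiatric condition that, in the opinion of the investigator, could jeopardize or would compromise" participation, has none either and leaves room for judgement. What escapes exclusion 10 is a serious infection that both began and resolved between Screening and Day 1.
- Inclusion 5a, 5b and 5d: a dose change in the gap satisfies the sub-item but conflicts with the stem. This is a mismatch between stem and sub-items.

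**3. Size, as an illustration.** Every biological input here is assumed; none is in the documents. Let A be the fractional disturbance of IgG at treatment, h its half-life, and d the days from treatment to Day 1. Week 7 falls 42 days after Day 1.

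- Baseline ratio = 1 + A·2^(-d/h)
- Week 7 ratio = 1 + A·2^(-(d+42)/h)
- Spurious change (%) = 100 × (Week 7 ratio / Baseline ratio - 1)

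Take d = 7 and h = 14, 21 or 28 days, in a placebo participant. The table gives the end points of each range.

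| Assumption | Baseline ratio | Week 7 ratio | Spurious change | Shift in mean of 7 |
|---|---|---|---|---|
| IVIG, A = +0.5, h = 28 | 1.420 | 1.149 | -19.1% | -2.7 |
| IVIG, A = +1.0, h = 14 | 1.707 | 1.088 | -36.2% | -5.2 |
| PE, A = -0.4, h = 28 | 0.664 | 0.881 | +32.8% | +4.7 |
| PE, A = -0.6, h = 21 | 0.524 | 0.881 | +68.2% | +9.7 |

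One such participant therefore moves the unadjusted placebo mean by about 3 to 10 points.

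A cruder model sets the Day 1 distortion directly and assumes full recovery by Week 7. Baselines lowered by 20, 40 or 60% give changes of +25, +67 or +150%, or +3.6, +9.5 or +21.4 points on the mean of 7. Baselines raised by 20, 30 or 50% give -2.4, -3.3 or -4.8 points. The range depends heavily on the assumptions.

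In the 680 mg arm (true change taken as -77.5%, the middle of the expected 75-80%), the same six distortions move the mean by only -1.1 to +4.8 points.

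**4. Would it change the test result?** The planning difference is 33 points with SD 20 (Protocol 10.1), but Protocol 3.2.2 expects reductions of 65-70% and 75-80%. A simulation used 7 v 7, SD 20, a true difference of 65 and a t-test, with one placebo value shifted by -36, +33 or +68 points. Power stays above 99% in each case.

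**The case against.** **The stem of inclusion 5 may cover IVIG and PE.** Protocol 3.1.1 lists both among the treatments MG patients maintain, so starting either after Screening could be read as breaking the stable-treatment requirement. Exclusion 18 might also be read to reach plasma-derived products, and Section 7.9.2 refers to a study reference manual that was not supplied. This part stands: it cannot be said with certainty that such a participant would be enrolled. But the detailed conditions of inclusion 5 concern drugs only, and exclusion 18 names neither treatment. The criterion written for this exposure should not depend on inference from others.

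**Existing safeguards.** Total IgG is drawn on Day 1, and an unblinded Medical Monitor reviews it on an ongoing basis. A low value would not necessarily go unseen, although nothing says the result is available before dosing. Concomitant medication is recorded from Screening, and SAP 6.3 lists receipt of an excluded treatment as a possible major deviation. That helps only if the treatment counts as excluded, which is the point in doubt. SAP 9.3 also allows the per-protocol analysis to be skipped when the sets differ by no more than 10%.

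**Analysis.** ANCOVA on baseline and rank-based sensitivity analyses are planned, and either may alter the shifts shown. This stands.

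**Stronger readings the documents do not support.** A reader might infer that all three Screening-anchored windows are equally open and all distort baseline IgG. They are not equally open (step 2 of the working), and nothing in the documents links an infection or an immunosuppressant change to a distorted Day 1 IgG. A reader might also see a contradiction between 60 days in exclusion 18 and 4 weeks in exclusion 3. Exclusion criteria are cumulative, so overlapping windows can both apply. What is unclear is the scope of exclusion 18.

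**Conclusion.** The gap in exclusion 3 is established from the text: up to 21 days before first dose in which immunoglobulin or PE does not meet the exclusion as worded. It matters because of the Day 1 denominator and the screening-only IgG floor. The gap in exclusion 10 is narrower, and the inclusion 5 point is one of internal consistency.

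The effect of about 3 to 10 points on the unadjusted placebo mean is conditional on one affected participant among 7, treatment on Day -7, and the assumed disturbances and half-lives. The documents give no rate of such treatment and do not show that any occurred. In arms of about 7, the main risk is a distorted estimate of the IgG effect. A reader might infer that the primary comparison could be overturned, but the expected 65-80% reduction makes that unlikely. Correcting the wording is worthwhile because it costs so little; sample size and power are unaffected.

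**What to change.** 1. In exclusions 3 and 10, keep the stated look-back lengths and extend the end of each window through first dose. The uncovered interval falls from up to 21 days to 0.
2. Align inclusion 5a, 5b and 5d with the stem of inclusion 5.
3. Have the sponsor state whether blood products in exclusion 18 include immunoglobulin or PE, and reconcile that with exclusion 3. Which window governs is for the sponsor to decide.
4. For participants already enrolled, flag any IVIG or PE between Screening and Day 1 at the blinded data review, and add a Week 7 IgG sensitivity analysis without them.

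Cost: a few words at the next amendment, one extra listing check and one extra analysis. The downside is a rare additional screen failure.

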#### **6.4. Eligibility for the OLE**

Participants who complete the 6-week, randomized, double-blind treatment phase are eligible to participate in the OLE.

#### **6.5. Other Eligibility Criteria Considerations**

To assess any potential impact on participant eligibility with regard to safety, the Principal Investigator must refer to the following document(s) for detailed information regarding warnings, precautions, contraindications, AEs, and other significant data pertaining to the investigational product(s) being used in this study:

RVT-1401 Investigator's Brochure

#### **6.6. Screening/Baseline Failures**

Screen failures are defined as participants who consent to participate in the clinical trial but are never subsequently randomized. A minimal set of screen failure information is required including demography, screen failure details, eligibility criteria, and any SAEs. Screen failure data will be recorded within the electronic Case Report Form (eCRF).

#### **6.7. Lifestyle Restrictions**

##### **6.7.1. Contraception**

Female participants of childbearing potential must not become pregnant and so must be sexually inactive by abstinence or agree to use a highly effective method of contraception (i.e., pregnancy rate of less than 1% per year).

###### **Abstinence**

Sexual inactivity by abstinence must be consistent with the preferred and usual lifestyle of the participant. Periodic abstinence (e.g., calendar, ovulation, symptothermal, postovulations methods) and withdrawal are not acceptable methods of contraception.

